2.3.3 Exploratory Efficacy Endpoints

The exploratory efficacy endpoints include the following:

• Cumulative days and time to discontinuation of supportive bladder care for HC, specifically continuous bladder irrigation and/or nephrostomy tubes.

- Summary of HC-associated signs and symptoms other than bladder pain, including urinary frequency, urinary urgency, constant need to urinate, and nocturia.
- Incidence and time to recurrence of HC, defined as two consecutive Bedi grades ≥2 with macroscopic hematuria (visibly bloody urine) that are at least 2 days apart.
- Incidence and time to recurrence of bladder pain.
- Requiring RBC and/or platelet transfusions and the number of required RBC and/or platelet transfusions (measured in transfusion units/participant).
- Change in renal function as assessed by eGFR. For participants requiring dialysis, number of days on dialysis will be captured.
- Time to resolution of BK viruria. Resolution of viruria will be defined by the lower limits of quantitation of the assay used.
- Viremia and viruria with each target virus (ie, BKV, AdV, CMV, HHV-6, JCV, and/or EBV) over time.
- Length of use of any pain medication(s) (IV, oral, or other), including antispasmodics, anticholinergics, and beta-3-agonists, used for control of lower abdominal/bladder pain.
- Use of immunosuppressive agents, by specific agent during the study.
- Number of hospitalizations, number of ICU stays, and number of days of ICU care for any reason.
- Use of antiviral therapies other than cidofovir with potential activity against at least one target virus by specific agent during the study.
- Overall survival, defined as time to death (from any cause) from the time of randomization in days.
- Incidence of relapse or progression of the primary malignancy.
- Overall quality of life as measured by EQ-5D questionnaires.
- Global impression of hemorrhagic cystitis change.

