Participants not observed to achieve resolution will be considered censored at their last study follow up. Definitive therapies to stop bladder bleeding, such as cystectomy, bladder vessel embolization, cauterization, fulguration, or formalin instillation are permitted. If it is given before or on the day of randomization, the participant will be included in the BK ITT analysis assuming a Bedi of 2 or above. If it is given post randomization, it will be considered treatment failure for the primary endpoint of time to resolution of macroscopic hematuria and will be censored at the last follow-up time of any participant. Participants who discontinued early from the study before

achieving resolution will be censored at the time of last follow up. Participants who died or took non-PSL VSTs prior to reaching resolution will be considered treatment failures and censored at the last follow-up time of any participant.

For Bedi assessments where the grade is not evaluable and the participant is receiving continuous bladder irrigation, has nephrostomy tubes that are uncapped, or the urine is visually bloody, macroscopic hematuria is considered unresolved. For all other Bedi assessments where the grade is not evaluable, the grade is considered missing.

The analysis date for a Bedi assessment is the visual assessment date. If there is no visual assessment date, the urine collection date will be used. Otherwise, the visit date will be used. One Bedi assessment will be selected per analysis date. If there are multiple Bedi assessments on the same analysis date, the worst case is selected. If for a visit, there are Bedi assessments with a visual assessment date or urine collection date, assessments with only a visit date will not be selected.

If there are multiple Hemostick scores on the same date, the highest score will be selected.

If the result of the primary efficacy endpoint (ie, time to resolution of macroscopic hematuria) is statistically significant based on the BK ITT Population, a formal hypothesis test will be conducted sequentially of this same endpoint based on the overall ITT Population using a one-sided 0.025 significance level.

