3.4.3 Other Efficacy Endpoints

If the result of the key secondary efficacy analyses based on the BK ITT and overall ITT Populations are both statistically significant, a formal hypothesis test will be conducted sequentially of the first other secondary endpoint, number of days in the hospital, based on the BK ITT Population. The analysis will be performed using a linear regression model with terms for treatment and the stratification factors at randomization (defined based on EDC data). This secondary endpoint will be tested at the one-sided 0.025 alpha level. If the result of the analysis based on the BK ITT Population is statistically significant, a formal hypothesis test of this endpoint will be conducted based on the overall ITT Population using a 0.025 alpha level. Supportive analyses will be conducted using the BK mITT, BK PP, and mITT Populations.

The sequential testing described above will control the overall Type I error for these endpoints at the one-sided 0.025 level.

Other continuous and categorical efficacy endpoints (including secondary and exploratory endpoints not selected for hierarchical testing above) will be summarized descriptively by treatment group using appropriate populations. Categorical endpoints will be summarized using the number and percentage of participants within each category.

Time-to-event endpoints will be summarized using Kaplan-Meier estimates. Treatment comparison using a stratified log-rank test adjusted by stratification factors at randomization (defined based on EDC data) at one-sided significance level 0.025 will be reported as well. In addition, the hazard ratio along with the 95% confidence intervals for the true hazard ratio will be calculated using a stratified Cox proportional hazards model with treatment, and other potentially confounding factors.

There is no adjustment for multiplicity in the analyses of these other efficacy endpoints.

Specifically, the following efficacy endpoints will be analyzed based on BK ITT Population unless mentioned otherwise, and equally at the one-sided 0.025 level.

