Cumulative days of supportive bladder care for HC, specifically continuous bladder irrigation and/or nephrostomy tubes, will be summarized by treatment group. In the analysis, cumulative days of supportive bladder care will include all days of such therapy for the entirety of the trial. Time to discontinuation refers to time from randomization to initial discontinuation of all supportive bladder care in participants who were receiving a supportive bladder care at randomization. Time to discontinuation of supportive bladder care for HC will be analyzed using Kaplan-Meier estimates, and treatment effect will be compared using stratified log-rank test and hazard ratio with stratified Cox proportional model.

HC-associated signs and symptoms other than bladder pain will be descriptively summarized. The signs and symptoms analyzed include urinary frequency, urinary urgency, constant need to urinate, and nocturia.

Incidence and time to recurrence of HC will be analyzed using Kaplan-Meier estimates, and treatment effect will be compared using stratified log-rank test and hazard ratio with stratified Cox proportional model. Only participants who have reached the HC resolution will be included in the analysis. Time to recurrence of HC refers to time from the HC resolution to the time when the initial Bedi grade to evaluate for recurrence demonstrates a Bedi Grade ≥2 with macroscopic hematuria.

Incidence and time to recurrence of bladder pain will be analyzed using the same methods. Only participants who have reached the bladder pain resolution will be included in the analysis. Time to recurrence of bladder pain refers to time from the bladder pain resolution to the time when the initial pain score exceeds "mild pain" without use of prescription pain medications or supportive bladder care.

The number of participants requiring RBC and/or platelet transfusions and the number of required RBC and/or platelet transfusions (measured in transfusion units/participant) will be summarized by treatment group.

Change in renal function as assessed by eGFR and number of days on dialysis for participants requiring dialysis will be summarized by treatment group.

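### Time to discontinuation of supportive bladder care has no durability or intercurrent-event rule, so a brief pause or a stop brought about by definitive therapy can count as a favourable event

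*SAP*

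**What the plan says.** SAP 2.3.3 lists the endpoint among the exploratory ones: "Cumulative days and time to discontinuation of supportive bladder care for HC, specifically continuous bladder irrigation and/or nephrostomy tubes". SAP 3.4.3 defines the time-to-event part as "time from randomization to initial discontinuation of all supportive bladder care", for participants already on such care at randomization, and states that "treatment effect will be compared using stratified log-rank test and hazard ratio with stratified Cox proportional model". The companion measure covers restarts: "cumulative days of supportive bladder care will include all days of such therapy for the entirety of the trial". Endpoints in this part of 3.4.3 are tested "equally at the one-sided 0.025 level", and the section adds: "There is no adjustment for multiplicity in the analyses of these other efficacy endpoints".

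The definition has no minimum time off, confirmation step or restart rule. It does not mention death, definitive therapy, non-PSL VSTs or dropout while on care.

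Rules for such events exist for other endpoints. For the primary endpoint, SAP 3.4.1 says "Participants who died or took non-PSL VSTs prior to reaching resolution will be considered treatment failures" and censors them at the last follow-up time of any participant. It handles post-randomization definitive therapy in the same way, but words that rule for the primary endpoint. The key secondary endpoint (SAP 3.4.2) has its own intercurrent-event table, which also takes in the primary endpoint's events. The global impression endpoint in 3.4.3 is analysed by analogy with the key secondary. The supportive-care endpoint refers back to neither.

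**The concern.** In this analysis an event is good news: the participant no longer needs irrigation or nephrostomy tubes. Two kinds of stop meet the written definition without being good news.

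- **A pause.** The word *initial* fixes the event at the first time all supportive care is off, even if care resumes the next day. SAP 2.3.1 asks for daily evaluation of whether irrigation can be stopped, so failed attempts are foreseeable.
- **A stop caused by definitive therapy.** If cystectomy, embolization or formalin instillation ends irrigation, the same procedure is a failure for the primary endpoint and a favourable event here.

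Death and non-PSL VSTs raise a different problem. The plan is silent, so a programmer must choose a coding. If the arms differ in mortality, that choice can change the direction of the bias. A hazard ratio and a nominal p-value will be reported whichever coding is used.

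**Working it through.** **No planned figure to reproduce.** The documents give no medians, event counts or power for this endpoint, so the check is a comparison of rules followed by an illustration.

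**Step 1: rules side by side.**

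| Feature | Primary (SAP 3.4.1) | Key secondary (SAP 3.4.2) | Stop of supportive care (SAP 3.4.3) |
|---|---|---|---|
| Confirmation | 2 consecutive Bedi grades at least 2 days apart | 2 consecutive pain scores | none |
| Definitive therapy after randomization | failure | among the primary's events taken in | not stated; literally an event if it ends care |
| Death | censored at last follow-up time of any participant | same | not stated |
| Non-PSL VSTs | failure | failure | not stated |

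**Step 2: hazard ratio if competing stops are coded as events.** Assumptions: constant hazards; medians of 12 weeks (placebo) and 6 weeks (PSL), borrowed from the primary endpoint's sample-size section (SAP 2.2.3) because none is given for this endpoint; and a 24-week risk p of a competing stop, which is in no document. The competing hazard per week is h = −ln(1 − p)/24, and the apparent hazard ratio is (λ₁ + h₁)/(λ₀ + h₀), where subscript 1 is PSL and 0 is placebo. Here ln2/6 = 0.11552 and ln2/12 = 0.05776. The competing hazards are 0.00439 at p = 10%, 0.00930 at 20% and 0.01486 at 30%.

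- True ratio 2.0, p = 10% in both arms: (0.11552 + 0.00439)/(0.05776 + 0.00439) = 1.93.
- True ratio 2.0, p = 20% in both arms: (0.11552 + 0.00930)/(0.05776 + 0.00930) = 1.86.
- True ratio 2.0, p = 30% placebo, 10% PSL: (0.11552 + 0.00439)/(0.05776 + 0.01486) = 1.65.
- No true effect (12 weeks in both arms), p = 10% placebo, 30% PSL: (0.05776 + 0.01486)/(0.05776 + 0.00439) = 1.17 in favour of PSL.

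Here p stands for any competing stop coded as an event. The formula does not separate death from definitive therapy.

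**Step 3: effect of the unstated death coding.** Unstratified log-rank simulation with 1,500 replicates, exponential times, 24 weeks, one-sided 0.025, an assumed 25 per arm at 1:1, and no true difference in stopping (median 12 weeks in both arms). The entries are the proportions of trials with a nominal finding for PSL.

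| 24-week mortality, placebo v PSL | Death = event | Censored at death | Failure to week 24 |
|---|---|---|---|
| 20% v 20% | 2.9% | 2.4% | 2.3% |
| 10% v 30% | 8.0% | 3.3% | 1.3% |
| 10% v 40% | 11.1% | 2.1% | 0.5% |
| 30% v 10% | 0.7% | 2.0% | 5.1% |

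With 15 per arm, 10% v 30% gives 6.6%, 2.9% and 1.3%. Monte Carlo standard error is √(0.025 × 0.975/1500) = 0.4 points near 2.5%, and √(0.08 × 0.92/1500) = 0.7 points near 8%. At equal mortality the coding hardly matters. With unequal mortality, coding death as an event favours the arm with more deaths, whichever that is. The 5.1% under failure coding is not a false signal in the same sense, because that endpoint is a composite and PSL has fewer deaths in that row.

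**Step 4: pauses.** No document gives a frequency of pauses or restarts, so their effect cannot be sized.

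**The case against.** A reader might infer that the plan counts a stop for any reason and scores death on irrigation as a success. The documents do not support that. SAP 3.4.3 never says so, and SAP 2.3.1 describes stopping irrigation as resting on clinical condition and the treating physician's judgement, which death is not. A recorded end date at death could be programmed as an event, but that would be a programming choice and not a stated rule. The death part is therefore a gap.

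Four further objections have weight:

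- **Rank.** The endpoint is exploratory, outside the hierarchy and restricted to a subset of unknown size. It cannot affect trial success or any gated test. This stands, and it sets the severity.
- **Restarts are captured elsewhere.** Cumulative days counts all care over the trial, and the event requires every modality to be off. This stands in part. Cumulative days is itself shortened by death, and it does not alter the hazard ratio or p-value for the first stop.
- **First occurrence is used elsewhere.** Time to resolution of BK viruria also uses the initial resolution. That is so, but the endpoints closest to this one (hematuria, pain, global impression) all require two consecutive results.
- **The illustrative rates are undocumented.** This stands. An excess of deaths large enough to mislead would also show in the planned survival and adverse event summaries.

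None of these answers the literal reading under which a brief complete pause, or a stop after cystectomy, is a favourable event.

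**Conclusion.** The point holds, at low severity. As written, the endpoint counts a transient complete stop as success, and also a stop produced by definitive therapy. The second conflicts with how the primary endpoint treats the same procedure. For death and non-PSL VSTs the plan is silent, which leaves three codings open. It cannot be read as scoring death as benefit.

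The size is conditional. With equal competing risks the distortion is modest and conservative (2.0 becomes 1.93 at 10%, or 1.86 at 20%), and the error rate stays near nominal. With unequal risks it can run either way: 1.65 in place of 2.0, or 1.17 in place of 1.0. These ratios illustrate one possible coding under assumed rates, constant hazards and medians borrowed from another endpoint. The simulation covers death only, with an assumed subset size and 1:1 allocation.

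**What to change.** Add two rules to the definition in SAP 3.4.3 before unblinding.

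1. The event is the first day of a sustained stop of all supportive bladder care, with the minimum time off set by the sponsor. The 2-day interval used to confirm hematuria resolution is an analogue within the SAP.
2. Post-randomization definitive therapy, death or non-PSL VSTs occurring before a sustained stop is established are failures, censored at the last follow-up time of any participant, as in 3.4.1. The censoring rule for dropout while on care should be stated in the same place.

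**Cost.** A few sentences, slightly more derivation work and somewhat later event dates. Protocol 6.6.2 already requires supportive care to be documented in the eCRF. No section says that the reason for stopping is collected, so the second rule should depend on the order of dates. The endpoint also becomes a composite in which mortality differences contribute, and the report should say so.

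### HC and pain recurrence are compared between arms by log-rank test and hazard ratio in resolvers only; this is not a randomized comparison, and its bias can go either way

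*SAP*

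**What the plan says.** SAP 3.4.3 (Other Efficacy Endpoints) analyses incidence and time to recurrence of HC by Kaplan-Meier and compares the arms by stratified log-rank test and stratified Cox hazard ratio, with this restriction: "Only participants who have reached the HC resolution will be included in the analysis". The clock starts at resolution, not randomization: "Time to recurrence of HC refers to time from the HC resolution". Pain recurrence uses the same methods, again restricted: "Only participants who have reached the bladder pain resolution will be included in the analysis". The pain event occurs when "the initial pain score exceeds 'mild pain' without use of prescription pain medications or supportive bladder care", and no confirming second score is mentioned.

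SAP 2.3.3 lists both endpoints as exploratory. SAP 3.4.3 places them outside the hierarchy ("There is no adjustment for multiplicity in the analyses of these other efficacy endpoints") but still gives these endpoints a test level, "equally at the one-sided 0.025 level". Neither SAP 2.3.3 nor SAP 3.4.3 says that the resolver-only comparison is non-randomized, and neither describes a companion recurrence or durability analysis in all randomized participants.

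**The concern.** HC resolution is the primary outcome and pain resolution the key secondary. If posoleucel works, its resolvers will include people who would not have resolved on placebo, so the two resolver groups need not be comparable. Stratifying by the randomization factors does not restore comparability. A log-rank test and hazard ratio labelled as a treatment effect invite the reader to treat them as randomized evidence.

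The primary endpoint counts first resolution only, so whether the response lasts is the natural next question. The protocol (2.3 and 7) listed resolution status at Weeks 2, 4, 6, 8 and 12, but SAP 2.3.3 does not carry it forward. The resolver-only analysis is therefore the SAP's only direct between-arm evidence on durability of hematuria resolution. An effective product could look worse or better on durability than it is.

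**Working it through.** **Inputs from SAP 2.2.3.** Median time to resolution 12 weeks (placebo) and 6 weeks (posoleucel); exponential; 24 weeks of follow-up; 20% censored by 24 weeks, exponential and equal in both arms; 105 in BK ITT; one-sided 0.025; stated power 86.4%. The allocation ratio is blacked out; 1:1 is assumed for counts (52.5 per arm).

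**Step 1: share observed to resolve.** With resolution rate λ = ln 2/median and dropout rate μ = −ln(0.8)/24 = 0.00930 per week, the probability is λ/(λ+μ) × (1 − e^(−24(λ+μ))).
- Posoleucel: λ = 0.1155; 0.1155/0.1248 × (1 − 0.0625 × 0.8) = 0.9255 × 0.95 = 0.879.
- Placebo: λ = 0.0578; 0.0578/0.0671 × (1 − 0.25 × 0.8) = 0.8614 × 0.80 = 0.689.

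**Step 2: check against the plan's own figure.** Expected events = 52.5 × (0.879 + 0.689) = 82.3. Schoenfeld power = Φ(√(82.3 × 0.25) × ln 2 − 1.96) = Φ(1.18) = 88.2%. The Freedman formula gives 85.6%, and simulation with a futility stop at conditional power below 5% gives 87.0%. All are within 2 points of 86.4%, so the inputs are read correctly. The documents state no figure for the recurrence analyses.

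**Step 3: who enters the recurrence analysis.** About 46 of 52.5 on posoleucel and 36 of 52.5 on placebo, a gap of 19 percentage points. Mean follow-up after resolution is 15.8 versus 13.9 weeks.

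**Step 4: resolver-only hazard ratio (posoleucel versus placebo) when treatment has no effect on recurrence.** Simulated with the inputs above. For HC, 25% recurrence over 24 weeks is assumed, and a log-normal participant effect links difficulty of resolving to recurrence where stated. None of these recurrence assumptions is in the documents.

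| Assumption | Hazard ratio |
|---|---|
| Recurrence unrelated to ease of resolution, constant hazard | 0.99–1.00 |
| Harder-to-resolve participants recur more | 1.04–1.16 |
| Harder-to-resolve participants recur less | 0.87–0.94 |
| Recurrence hazard falls with study time | 1.13 |
| Falling hazard, and harder cases recur more | 1.17 |

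In the first row, crude recurrence among resolvers is still higher in the faster arm (16.9% versus 15.2%), purely because follow-up is longer. The log-rank test and hazard ratio absorb this by censoring. Across the five rows at N = 105, the one-sided error is 1.0–3.7% against posoleucel and 1.5–5.1% in its favour, against a nominal 2.5%.

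**Step 5: surveillance density.** SAP 3.4.2 has worst pain recorded daily for six weeks and weekly thereafter. If pain resolved with the same medians (6 and 12 weeks; an assumption, since the documents give none for pain), 55% of posoleucel resolvers and 41% of placebo resolvers would have resolved by Week 6, so the earlier arm spends more post-resolution time under daily scoring. Giving every score the same chance of exceeding mild in both arms (0.5% to 2% per score) yields hazard ratios of 1.13–1.14 against the earlier arm. A uniform weekly schedule (5% per score) yields 0.99.

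For HC the same mechanism is weaker. In resolved outpatients, Bedi checks go from weekly to Weeks 12 and 24 after Week 6 (SAP Table 1), but weekly Hemostick monitoring continues, and resolved inpatients keep weekly Bedi checks.

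**The case against.** Recurrence can only follow resolution, so a resolver-only display is natural. The endpoints are exploratory and unadjusted, and nothing in the primary claim depends on them. Whole-trial burden measures that do not condition on resolution are already planned: hospital days, cumulative days of supportive bladder care, transfusions and pain-medication days. All of this stands, and it limits the weight of the point. Those measures do not, however, show directly whether resolution lasts.

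The likely bias is also small against sampling error. With 46 and 36 resolvers and the crude rates in Step 4, about 46 × 0.169 = 7.8 and 36 × 0.152 = 5.5 recurrences are expected. The standard error of the log hazard ratio is about √(1/7.8 + 1/5.5) = 0.56, and ln 1.17 = 0.16 is under 0.3 of that. This stands too: the problem is one of interpretation, not of a test likely to mislead often.

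A reader might infer that the analysis is necessarily biased against the arm that resolves more and earlier. The documents do not support that. No section links ease of resolution to recurrence risk, and the reverse relation moves the hazard ratio in favour of posoleucel. Nor does longer post-resolution follow-up by itself bias an analysis timed from resolution with censoring; it affects only crude incidence.

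**Conclusion.** The point holds as a minor one. Both recurrence comparisons are made in subsets defined by an outcome that treatment is expected to change, with about 88% versus 69% entering the HC analysis under the SAP's own assumptions. Neither the log-rank p-value nor the hazard ratio can be read as a randomized treatment effect.

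The direction of bias is open: about 0.87 to 1.17 with no true effect. It runs against the earlier-resolving arm if harder cases recur more, if recurrence hazard falls with study time, or if early surveillance is denser. Only the last rests on the documents' own schedule, and it is best supported for pain.

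The resolver shares rest on SAP 2.2.3. The counts add 1:1 allocation; the hazard ratios add the assumed recurrence rates, severity relations and pain medians. The primary test and the testing hierarchy are unaffected.

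**What to change.** In SAP 3.4.3, label the resolver-only Kaplan-Meier results for HC and pain recurrence as descriptive and non-randomized, with no p-value and no treatment-effect reading of the hazard ratio.

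Add one exploratory comparison from randomization in all BK ITT participants, for example the probability of being alive, resolved and recurrence-free without definitive therapy through Week 24. State how participants without Week 24 status are handled, by censoring or another missing-data rule, because the SAP assumes 20% are lost by then. Show the resolution and recurrence components separately.

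The cost is a little more analysis on data already collected. The drawback is that the composite mixes speed of resolution with durability and so partly repeats the primary endpoint, which is why the components must be shown. Recurrence dates in resolved outpatients will also be coarse after Week 6, given the scheduled Bedi checks.
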